3.0 STUDY POPULATION

3.1 Inclusion Criteria

1. Undergoing standard of care colonoscopy for the evaluation of colonic polyps.
2. At least 40 years of age.
3. Ability to understand and willingness to sign an IRB approved written informed consent document (or that of legally authorized representative, if applicable).

3.2 Exclusion Criteria

1. Pregnant and/or breastfeeding.
2. Unable to tolerate sedation.

3.3 Inclusion of Women and Minorities

Both men and women and members of all races and ethnic groups are eligible for this trial.

4.0 REGISTRATION PROCEDURES

Patients must not start any protocol intervention prior to registration through the Siteman Cancer Center.

The following steps must be taken before registering patients to this study:

1. Confirmation of patient eligibility
2. Registration of patient in the Siteman Cancer Center database
3. Assignment of unique patient number (UPN)

4.1 Confirmation of Patient Eligibility

Confirm patient eligibility by collecting the information listed below:

1. the registering MD's name
2. Patient's race, sex, and DOB
3. Three letters (or two letters and a dash) for the patient's initials
4. Copy of signed consent form
5. Completed eligibility checklist, signed and dated by a member of the study team
6. Copy of appropriate source documentation confirming patient eligibility

4.2 Patient Registration in the Siteman Cancer Center OnCore Database

All patients must be registered through the Siteman Cancer Center OnCore database.

4.3 Assignment of UPN

Each patient will be identified with a unique patient number (UPN) for this study. All data will be recorded with this identification number on the appropriate CRFs.

4.4 Screen Failures

Screen failures are defined as participants who consent to participate in the clinical trial but are not subsequently entered in the study. A minimal set of screen failure information is required to ensure transparent reporting of screen failure participants, to meet the Consolidated Standards of Reporting Trials (CONSORT) publishing requirements and to respond to queries from regulatory authorities. Minimal information includes demography, screen failure details, eligibility criteria, and any serious adverse event (if applicable).

5.0 STUDY PROCEDURES

5.1 Recruitment

Adult patients scheduled to undergo a routine colonoscopy for screening or surveillance of colon polyps, evaluation of GI bleeding, post-colon cancer resection surveillance, or reassessment of prior colon polyp will be screened for the study. Patients will be identified as candidates for the study from the BJH Surgery schedule the day before they come in. One of the investigators or a research assistant will discuss the study with potential participants in the pre-endoscopy area. Those subjects who qualify for the study based on eligibility criteria will be invited to participate. The consent process will take place in the

pre-endoscopy area. Those patients who wish to participate will sign the informed consent document and proceed to colonoscopy.

5.2 Study Procedures

After consent, the endoscopist will perform a standard of care colonoscopy. We will enroll 54 participants in the study and expect approximately 40 of these participants to have polyps. If a polyp is found, then OCT will be used to image that polyp. Patients with polyps, regardless of number found, will have either one tubular adenoma (NICE type 2) imaged OR one hyperplastic polyp (NICE type 1) imaged. These polyps can be distinguished endoscopically using the NICE classification (see Section 12, Figure 1). If no polyps are found, then one area of normal mucosa will be imaged. We will have a goal of imaging an equal number of tubular adenomas and hyperplastic polyps. We will have a running log of the number of imaged tubular adenomas and hyperplastic polyps imaged to ensure that equal amounts of each type are imaged. If on the rare chance a malignant appearing colonic tumor (NICE type 3) is found, this and no other polyps will be imaged with OCT.

Duration of using OCT probe as well as duration of the colonoscopy will be kept by endoscopy staff with a stopwatch. Initiation of colonoscopy will be time 00:00. There will then be time marks for initiation of OCT imaging, end of OCT imaging, and end of colonoscopy. In this way, the exact duration of OCT and the full duration of colonoscopy with OCT will be captured.

Duration of OCT imaging will be from the time of guiding the OCT probe through the colonoscope to imaging, and withdrawal of OCT probe. The maximum time allotted to obtain OCT imaging will be 10 minutes. Any OCT imaging that reaches the 10-minute mark will be stopped so that routine colonoscopy can resume. A log of total procedure duration is kept for every standard of care colonoscopy.

When a polyp or area of normal mucosa to be examined with OCT is identified, the location of the area imaged will be documented (sigmoid, descending colon, transverse colon, ascending colon, cecum, etc.) by a registered nurse. The OCT catheter probe will be guided through the instrument channel of the colonoscope with the colonoscope still in the patient. This will take under approximately 5 seconds. The OCT probe will then be moved to make contact with the mucosa. The probe will then take several hundred high-resolution images of the lesion, with an expected duration of 2-3 minutes. During this time, the endoscopist will maintain view of the lumen and/or polyp. After completion of OCT imaging, the OCT probe will be removed, which will take approximately under 5 seconds. Colonoscopy will then resume to complete a full routine examination.

All procedures will be performed by a gastroenterologist experienced in advanced imaging techniques or by a fellow under direct supervision.

There will be a toxicity assessment at baseline and at the observation period after colonoscopy. Patients will also be contacted by phone approximately 48 hours after colonoscopy to collect information on any AEs experienced.

The standard of care pathology report for any area biopsied will be accessed from the medical record when available in order to compare the pathological findings with the diagnosis determined by OCT imaging.

5.3 Definitions of Evaluability

A patient must have had at least one colonic polyp or area of normal mucosa selected for OCT imaging in order to be evaluable for the feasibility endpoint. Any patient who does not have any area of mucosa imaged by OCT (either due to poor bowel prep, anesthesia complications, etc.), will be considered inevaluable for the feasibility endpoint and will be replaced.

All patients who undergo colonoscopy using the OCT probe are evaluable for toxicity and evaluation of imaging quality. Patients are evaluated for AEs from time of colonoscopy until 48 hours after colonoscopy.

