10.2 Endpoints

Primary endpoint is whether a lesion can be adequately evaluated with OCT within 5 minutes during a standard of care colonoscopy. If the proportion of the patients whose procedure length using an OCT probe during routine colonoscopy is within 5 minutes is greater than 75%, then the feasibility is defined in this study.

Secondary endpoints include:

- AEs related to OCT imaging during routine colonoscopy
- Whether OCT image is successfully captured using machine learning algorithm, coded as “good” or “noisy”. The OCT imaging catheter will be calibrated before each patient study to ensure that the catheter system is working properly. In an in vivo study of the catheter, we expect some images will be distorted due to patient movement, sub-optimal contact with the mucosa, etc. The machine learning algorithm will judge image quality based on number of colonic crypts visualized (see Section 12, Figure 5). We hypothesize that the proportion of good OCT images is greater than 90%.
- Weighted Kappa. Clinical pathology is the gold standard for diagnosis. Diagnosis from both OCT and clinical pathology will be assigned as normal mucosa, hyperplastic polyp, tubular adenoma, sessile serrated adenoma, or colorectal cancer. Based on ex vivo data from [name] lab, we hypothesize that there will be an over 80% agreement rate in this feasibility study.

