10.3 Sample Size Calculation

The sample size calculation is based on the primary endpoint of feasibility only. The primary hypothesis is that the proportion of the patients who have OCT imaging which adds 5 minutes or less to the duration of standard of care colonoscopy is greater than 75%. The null hypothesis for feasibility is 75% and the alternative hypothesis is 90%. $H_0: p < 75\%$ $H_a: p > 75\%$ (expect it to be 90% in clinical practice). A sample size of 54 patients achieves 80.1% power to detect a difference of 15% using a two-sided exact test at a significance level of 5% with the assumption that the proportion is 75%.

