10.5 Statistical Analyses

10.5.1 Patient Disposition

The number of patients discontinued, the reasons for discontinuation, and the duration of OCT imaging administered will be summarized by patient and by reason for discontinuation.

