10.5.4 Endpoint Analysis

Proportions of the patients whose procedure length using an OCT probe during routine colonoscopy is within 5 minutes and who have good OCT images, as judged by a machine learning algorithm, will be provided. Their associated 95% confidence intervals (CIs) will be calculated assuming a binomial distribution. The descriptive statistics will be presented including frequency, type, and severity of AEs related to OCT imaging during routine colonoscopy. Weighted kappa and 95% CI will be computed for the agreement between OCT imaging and pathology for all enrolled patients. All analyses will be conducted using SAS (SAS Institute, Cary, NC) at the two-sided 5% significance level.

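### Section 5.3 does not say whether an OCT attempt that fails for device or technical reasons counts against feasibility; read literally, it is replaced

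*Combined protocol and SAP*

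**What the plan says.** Three rules bear on who is counted.

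- **Evaluability for feasibility (section 5.3, first paragraph).** The first sentence requires that a polyp or an area of normal mucosa was selected for OCT. The second sentence turns on a different event: "Any patient who does not have any area of mucosa imaged by OCT (either due to poor bowel prep, anesthesia complications, etc", and such a patient "will be considered inevaluable for the feasibility endpoint and will be replaced".
- **Evaluability for safety and image quality (section 5.3, second paragraph).** Here the trigger is use of the probe: "All patients who undergo colonoscopy using the OCT probe are evaluable for toxicity and evaluation of imaging quality".
- **The endpoint.** Section 10.2 opens with adequacy and time together: "Primary endpoint is whether a lesion can be adequately evaluated with OCT within 5 minutes during a standard of care colonoscopy". Its second sentence, which defines when feasibility is met, uses time only, as does the hypothesis in section 10.3. Section 10.5.4 will report "Proportions of the patients whose procedure length using an OCT probe during routine colonoscopy is within 5 minutes", again on time.

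Section 5.2 says when the clock runs: "Duration of OCT imaging will be from the time of guiding the OCT probe through the colonoscope to imaging, and withdrawal of OCT probe". It stops imaging at 10 minutes without saying how a stopped attempt is scored. Section 10.5.1 adds a disposition summary: "The number of patients discontinued, the reasons for discontinuation, and the duration of OCT imaging administered will be summarized".

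**The concern.** The two sentences of section 5.3 pull apart for one kind of patient: a site was selected, the probe was introduced, and no image was obtained because of the device or the technique. The first sentence admits this patient and the second removes and replaces them. Nothing in sections 10.2, 10.3, 10.5.1 or 10.5.4 puts them back into the primary proportion.

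This patient is the clearest failure of the endpoint as section 10.2 first states it. If such patients are replaced, the study estimates success given that an image was obtained, which is at least as high as success over all attempts. The study is also meant to identify modifications to the device (protocol summary), so these are the cases it most needs to count.

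The time-only definitions create a second gap. If the patient were kept and scored on elapsed time alone, a quick attempt with no image could count as a success. So neither replacing nor retaining such a patient gives the right answer without a written rule.

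**Working it through.** **1. Inputs.** Null 75%, alternative 90%, N = 54, two-sided exact test at 5% (section 10.3). The share f of attempts that give no image for device or technical reasons is not in the documents. It is assumed here at 0% to 5%.

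**2. The plan's own figure.** Section 10.3 states: "A sample size of 54 patients achieves 80.1% power to detect a difference of 15% using a two-sided exact test". The normal approximation gives Φ[(0.15 − 1.96·√(0.75·0.25/54)) / √(0.9·0.1/54)] = Φ[(0.15 − 1.96·0.0589)/0.0408] = 0.801, which matches. The exact binomial test gives:

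- P(X ≥ 46 | 54, 0.75) = 0.0525, above 0.025
- P(X ≥ 47 | 54, 0.75) = 0.0241, so the cut-off is 47/54
- power P(X ≥ 47 | 54, 0.90) = 0.832

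The exact rule is used below.

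**3. Effect of replacement.** Let true success over all attempts be 75%, with no-image attempts counted as failures. If they are replaced until 54 evaluable patients are reached, the rate among those 54 is 0.75/(1 − f). The expected number replaced is 54/(1 − f) − 54.

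| f (assumed) | Rate among the 54 | Expected replaced | P(X ≥ 47) |
|---|---|---|---|
| 0% | 0.7500 | 0 | 2.4% |
| 1% | 0.7576 | 0.5 | 3.2% |
| 2% | 0.7653 | 1.1 | 4.2% |
| 5% | 0.7895 | 2.8 | 9.4% |

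The benchmark is the 2.5% upper tail of the two-sided test. At f = 5%, no-image cases would be 0.05/0.25 = 20% of all failures.

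**4. One case at the boundary.** The exact 95% lower limit for 47/54 is 75.1%. If one of those 54 places had been held by a no-image failure instead of a replacement who succeeded, the result would be 46/54, with a lower limit of 72.9%.

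**5. Retained but scored on time alone.** If every no-image attempt were kept and was quick, the rate would be 0.75 + f, and P(X ≥ 47) would be 5.0% at f = 2% and 12.8% at f = 5%. This effect comes from the time-only definition, not from replacement.

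**6. Effect of counting these attempts as failures on power.** If the 90% describes imaged patients only, success over all attempts is 0.90(1 − f). Exact power at N = 54 is then 83.2% at f = 0, 76.9% at 1%, 69.7% at 2% and 46.8% at 5%. If the 90% already covers all attempts, power stays at 83.2%.

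**The case against.** **The authors probably meant patients in whom OCT was never attempted.** Both named causes, bowel preparation and anesthesia, are unrelated to the device, and the first sentence of section 5.3 asks only for a selected site. This is a natural reading and may be the intended one. It does not settle the matter: selection is worded as a necessary condition, while the next sentence is a categorical exclusion based on imaging, with an open list of causes.

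**Every operational definition is time-only.** This stands. Against the second sentence of section 10.2, and against sections 10.3 and 10.5.4, replacing a quick no-image attempt does not inflate the result. The upward bias is relative to the endpoint sentence that requires adequate evaluation.

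**The 47/54 rule is not written in the plan as the decision rule.** Also true. Section 10.2 taken literally needs only a proportion above 75%, which is 41/54 (0.75 × 54 = 40.5). At a true 75% that rule is met with probability 51% even when f = 0, and 61% with replacement at f = 2%. The figures above therefore illustrate the section 10.3 test only.

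**Replaced patients may be visible anyway.** Section 10.5.1 reports discontinuations and reasons, but it does not name replacements or alter the primary proportion.

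A reader might go further and infer that the plan sets out to discard device failures, or that slow and poor-quality cases are dropped too. The documents support neither. The named causes point away from the first. As to the second, a case over 5 minutes or with a noisy image has been imaged and stays in the denominator.

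**Conclusion.** The point holds as an internal tension in section 5.3 that should be fixed. Followed literally, the rule takes no-image attempts with a device or technical cause out of the primary denominator and keeps them for toxicity and image quality. It then biases the proportion upward against the adequacy endpoint.

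The size is unknown because f is unknown. On the stated assumptions the chance of declaring feasibility at a true 75% rises modestly at f = 1% to 2% and to nearly four times its f = 0 value at 5% (9.4/2.4 = 3.9). There is no bias if no such attempts occur or if replacement is confined to non-device causes. A claim that the trial's false-positive rate is in fact inflated would go beyond the documents, which give no failure rate and do not say which reading applies.

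**What to change.** In sections 5.3 and 10.5.4:

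- Define the feasibility denominator as all patients in whom the OCT probe was introduced into the colonoscope channel, the point where the section 5.2 clock starts.
- Count an attempt with no image for device or technical reasons as a failure, whatever the elapsed time.
- Limit replacement to patients in whom OCT was not attempted, or in whom a cause unrelated to the device, such as those section 5.3 names, prevented imaging. This keeps an anesthesia complication after introduction from being scored as a device failure.
- Report the number replaced and the reasons beside the primary proportion.
- Add a sensitivity analysis that counts every no-image attempt after introduction as a failure.

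The cost is wording in two sections, plus a record of whether OCT was attempted and why no image was obtained. That record could sit on the OCT Data Form or the Colonoscopy Procedure Form; section 7.0 lists the forms but not their fields. The observed rate may be less favourable. The study team should also say whether the 90% in section 10.3 refers to all attempts or to imaged patients only, since power falls under the second reading and is unchanged under the first.

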6.0 REGULATORY AND REPORTING REQUIREMENTS

The entities providing oversight of safety and compliance with the protocol require reporting as outlined below. Please refer to Appendix A for definitions and Appendix B for a grid of reporting timelines.

Adverse events will be tracked from time of colonoscopy through 48 hours after end of colonoscopy. All adverse events must be recorded on the toxicity tracking case report form (CRF) with the exception of:

- Baseline adverse events, which shall be recorded on the medical history CRF

Refer to the data submission schedule in Section 7 for instructions on the collection of AEs in the EDC.

Reporting requirements for Washington University study team may be found in Section 6.1.

6.1 WU PI Reporting Requirements

6.1.1 Reporting to the Human Research Protection Office (HRPO) at Washington University

Reporting will be conducted in accordance with Washington University IRB Policies.

Pre-approval of all protocol exceptions must be obtained prior to implementing the change.

6.1.2 Reporting to the Quality Assurance and Safety Monitoring Committee (QASMC) at Washington University

The PI (or designee) is required to notify the QASMC of any unanticipated problems involving risks to participants or others occurring at WU or any BJH or SLCH institution that has been reported to and acknowledged by HRPO. (Unanticipated problems reported to HRPO and withdrawn during the review process need not be reported to QASMC.)

QASMC must be notified within **10 days** of receipt of IRB acknowledgment via email to [contact]. Submission to QASMC must include the myIRB form and any supporting documentation sent with the form.

6.2 Exceptions to Expedited Reporting

Events that do not require expedited reporting as described in Section 6.1 include:

- planned hospitalizations
- hospitalizations < 24 hours
- respite care
- events related to disease progression

Events that do not require expedited reporting must still be captured in the EDC.

7.0 DATA SUBMISSION SCHEDULE

Case report forms with appropriate source documentation will be completed according to the schedule listed in this section.

Case Report Form	Submission Schedule
Original Consent Form	Prior to registration
On-Study Form Medical History Form	Prior to colonoscopy
Colonoscopy Procedure Form OCT Data Form	Following colonoscopy
Toxicity Form	Baseline Post-colonoscopy observation period 48 hours following colonoscopy

7.1 Adverse Event Collection in the Case Report Forms

All adverse events that occur beginning with colonoscopy (minus exceptions defined in Section 6.0) must be captured in the Toxicity Form. Baseline AEs should be captured on the Medical History Form.

8.0 SCHEDULE OF ACTIVITIES

	Screening	Colonoscopy	48 hours after colonoscopy
Informed consent	X		
Pregnancy test ¹		X	
Colonoscopy		X	
AE monitoring		X	X

1. Women of childbearing potential only

9.0 DATA AND SAFETY MONITORING

In compliance with the Washington University Institutional Data and Safety Monitoring Plan, the Principal Investigator will provide a Data and Safety Monitoring (DSM) report to the Washington University Quality Assurance and Safety Monitoring Committee (QASMC) semi-annually beginning six months after accrual has opened (if at least one patient has been enrolled) or one year after accrual has opened (if no patients have been enrolled at the six-month mark).

The Principal Investigator will review all patient data at least every six months, and provide a semi-annual report to the QASMC. This report will include:

- HRPO protocol number, protocol title, Principal Investigator name, data coordinator name, regulatory coordinator name, and statistician
- Date of initial HRPO approval, date of most recent consent HRPO approval/revision, date of HRPO expiration, date of most recent QA audit, study status, and phase of study
- History of study including summary of substantive amendments; summary of accrual suspensions including start/stop dates and reason; and summary of protocol exceptions, error, or breach of confidentiality including start/stop dates and reason
- Study-wide target accrual and study-wide actual accrual
- Protocol activation date
- Average rate of accrual observed in year 1, year 2, and subsequent years
- Expected accrual end date
- Objectives of protocol with supporting data and list the number of participants who have met each objective
- Early stopping rules with supporting data and list the number of participants who have met the early stopping rules
- Summary of toxicities
- Abstract submissions/publications
- Summary of any recent literature that may affect the safety or ethics of the study

The study principal investigator and Research Patient Coordinator will monitor for serious toxicities on an ongoing basis. Once the principal investigator or Research Patient Coordinator becomes aware of an adverse event, the AE will be reported to the HRPO and QASMC according to institutional guidelines.

10.0 STATISTICAL CONSIDERATIONS

10.1 Study Design

This is a one-arm non-blinded study to investigate the feasibility of an OCT probe for patients undergoing routine screening or surveillance colonoscopy. The primary objective is to demonstrate the procedural feasibility of OCT during routine colonoscopy. Secondary objectives aim to describe the safety of the OCT probe, evaluate the quality of OCT images using a machine learning algorithm, and explore the diagnosis agreement between OCT imaging and pathology when a lesion is biopsied. OCT imaging through a catheter directed probe during routine colonoscopy will be measured by the duration of the entire procedure as well as duration of the OCT procedure itself.

